3.3 CLINICAL ASSESSMENTS

3.3.1 Efficacy

There are no efficacy measures since this is an observational study.

3.3.2 Safety

Overall safety during the conduct of the study will be assessed on the following parameters: AEs, vital sign measurements, concomitant medications, and oxygenation.

3.3.2.1 Medical History and Demographics

A complete medical history (inclusive of PAH and World Health Organization [WHO] Functional Class) and demographics will be collected during Screening. Any known changes to the medical history prior to enrollment should be recorded. Significant past or present illnesses, current prescription or nonprescription medications (including vitamins and herbal products), and history of allergies or idiosyncratic responses to drugs should be recorded. Any significant changes to the subject's medical condition must be documented throughout the course of the study.

3.3.2.2 Vital Signs

Vital signs will include SBP and DBP. HR will be collected via continuous pulse oximetry (Section 3.3.2.3). Vital signs will be collected at the beginning and at the end of each clinic visit.

3.3.2.3 Oxygenation (Pulse Oximetry)

Pulse oximetry will be performed from the beginning of pre-ISWT (15 minutes prior to the ISWT) and will be continuous through the end of recovery. Pulse oximetry will include the collection of saturation of peripheral capillary oxygenation (SpO₂) and HR. The SpO₂ and HR measurements obtained at -15 and 0 minutes (prior to activity), every minute during the ISWT, every minute for the first 5 minutes of the recovery, followed by every 5 minutes for the remainder of the 30-minute recovery, will be recorded in the subject's source documents and electronic Case Report Form (eCRF).

A specific pulse oximeter model will be recommended by the Sponsor and the site will purchase and provide the Sponsor an invoice for reimbursement. In the event a pulse oximeter cannot be used (ie, subject has known issues with obtaining accurate readings from a finger probe, etc), an alternative device may be used with prior Sponsor approval, so long as the same device is used throughout the study.

3.3.2.4 *Adverse Events*

Adverse events will be recorded throughout the course of the study from the time of informed consent until the time a subject discontinues or subject completes the study. Each subject will be questioned for AEs at each study visit. Subjects will also be instructed to voluntarily report all AEs throughout the study.

All AEs should be followed until resolution (or return to normal or baseline values), until they are judged by the Investigator to no longer be clinically significant, or for at least 7 days if the AE extends beyond the end of study assessments. All AEs meeting criteria for a serious adverse event (SAE) should be followed until resolution, death, or until the subject is lost to follow-up, even if they are ongoing more than 7 days after study completion. All AEs/SAEs that occur while the subject is in the study will be recorded as instructed in this protocol.

Section 9 and Appendix 15.4 provide definitions and guidelines for recording AEs, respectively.

3.3.3 *Concomitant Medications*

All concomitant medications taken throughout the course of the study, including those taken for AEs, should be recorded in the subject's source documents and captured in the eCRF as required.

3.3.4 *Assessment of PGI-S Questions and Borg Dyspnea Scores*

3.3.4.1 *Incremental Shuttle Walk Test*

The ISWT is the activity that will be used to induce symptoms of PAH during Screening and on Day 1 of the study. All activities will be conducted in a designated area which meets the requirements described in Appendix 15.2.

Subjects receiving supplemental oxygen during the Screening assessment must continue to receive the same flow rate at all subsequent ISWTs. The supplemental oxygen flow rate must be recorded for each activity, as applicable. Supplemental oxygen therapy must not be introduced for subjects after the Screening assessment, unless there is an urgent medical need in the clinical judgement of the Investigator.

The total number of shuttles completed by a subject during the Screening ISWT will be the maximum targeted for that subject during the remaining ISWTs in the study.

3.3.4.2 PGI-S Questions

Three PGI-S questions will be administered at pre-ISWT (-15 and 0 minutes prior to activity inducement of PAH symptoms), immediately at the end of the ISWTs (within 1 minute of completing the activity), every minute for the first 5 minutes of recovery followed by every 5 minutes for the remainder of the 30-minute recovery. Assessments will be recorded in the subject's source documents and eCRF.

PGI-S assessments will be performed in the following order prior to the Borg dyspnea score assessment:

3.3.4.3 Borg Dyspnea Score

The Borg dyspnea score (Appendix 15.3) is a 10-point scale rating the level of dyspnea experienced during the study-defined activity and is administered at each clinic visit at pre-ISWT (-15 and 0 minutes prior to activity inducement of PAH symptoms) and immediately at the end of the ISWTs (within 1 minute of completing the activity). Scores range from 0 (no shortness of breath) to 10 (maximal shortness of breath). Assessments will be recorded in the subject's source documents and eCRF.

3.4 NUMBER OF CENTERS

Up to 20 US centers that treat PAH subjects will be identified and recruited for this study.

3.5 NUMBER OF SUBJECTS

The total sample size will be approximately 40 subjects to ensure at least 36 evaluable subjects complete the study.

3.6 ESTIMATED STUDY DURATION

The total study duration for a subject, including the Screening Period, will be up to 15 days.

4 SUBJECT ELIGIBILITY

4.1 INCLUSION CRITERIA

Subjects who meet the following criteria may be included in the study:

1. Subject voluntarily gives informed consent to participate in the study.
2. Males and females aged 18 years and above at the time of informed consent.
3. Established primary diagnosis of PAH that is either idiopathic or familial PAH (WHO Group 1), collagen vascular disease associated PAH, PAH associated with human immunodeficiency virus (HIV) infection, PAH induced by anorexigens/toxins, or PAH associated with repaired congenital systemic-to-pulmonary shunts (repaired ≥ 1 years).
4. Subject is deemed WHO Functional Class I, II, or III.
5. Subject has shortness of breath upon exertion (exhibits a ≥ 1 -point change in Borg dyspnea score) as assessed by the ISWT and a minimum completion of 3 shuttles (30 meters) of the ISWT. Subject may have other symptoms as well.
6. Subject is on stable dose of all FDA-approved PAH treatments (exceptions are anticoagulants and diuretics) for at least 60 days prior to Screening.
7. In the opinion of the Investigator, the subject can communicate effectively with study personnel, and is considered reliable, willing, and likely to be cooperative with protocol requirements.

4.2 EXCLUSION CRITERIA

The following will exclude subjects from the study:

1. The subject is known to be pregnant or nursing.
2. The subject has PAH related to any condition not covered under inclusion criteria, including, but not limited to, pulmonary venous hypertension, pulmonary veno-occlusive disease, pulmonary capillary hemangiomatosis, chronic thromboembolic pulmonary hypertension, or other conditions under WHO Group 2, 3, 4, and 5 classifications.
3. The subject has evidence of clinically significant left-sided heart disease (including, but not limited to, left ventricular ejection fraction $<40\%$, left ventricular hypertrophy)

or clinically significant cardiologic conditions, such as congestive heart failure, coronary artery disease, or valvular heart disease.

4. The subject has any form of congenital heart disease (repaired or unrepaired; other than a patent foramen ovale).
5. The subject has any ambulatory or orthopedic limitations that would interfere with the ability to perform the activity.
6. The subject has been hospitalized within 30 days of Screening.
7. Current use of prostacyclin analogs/agonists, except inhaled treprostinil, for the treatment of PAH.
8. Use of any other investigational drug/device, or participation in any investigational study with therapeutic intent within 30 days of Screening (concurrent participation in registry studies is allowed).
9. Any other clinically significant illness that, in the opinion of the Investigator, might put the subject at risk of harm during the study or might adversely affect the interpretation of the study data.

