Summary of Subject Eligibility Criteria	
Inclusion criteria:
 
Subjects who meet the following criteria may be included in the study:
 
1. Subject voluntarily gives informed consent to participate in the study.2. Males and females aged 18 years and above at the time of informed consent.3. Established primary diagnosis of PAH that is either idiopathic or familial PAH (World Health Organization [WHO] Group 1), collagen vascular disease associated PAH, PAH associated with human immunodeficiency virus (HIV) infection, PAH induced by anorexigens/toxins, or PAH associated with repaired congenital systemic-to-pulmonary shunts (repaired ≥ 1 year).4. Subject is deemed WHO Functional Class I, II, or III.5. Subject has shortness of breath upon exertion (exhibits a ≥ 1-point change in Borg dyspnea score) as assessed by the ISWT and a minimum completion of 3 shuttles (30 meters) of the ISWT. Subject may have other symptoms as well.

6. Subject is on stable dose of all prescribed FDA-approved PAH treatments (exceptions are anticoagulants and diuretics) for at least 60 days prior to Screening.
7. In the opinion of the Investigator, the subject can communicate effectively with study personnel and is considered reliable, willing, and likely to be cooperative with protocol requirements.

Exclusion Criteria:

The following will exclude potential subjects from the study:

1. The subject is known to be pregnant or nursing.
2. The subject has PAH related to any condition not covered under inclusion criteria, including, but not limited to, pulmonary venous hypertension, pulmonary veno-occlusive disease, pulmonary capillary hemangiomatosis, chronic thromboembolic pulmonary hypertension, or other conditions under WHO Group 2, 3, 4, and 5 classifications.
3. The subject has evidence of clinically significant left-sided heart disease (including, but not limited to, left ventricular ejection fraction <40%, left ventricular hypertrophy) or clinically significant cardiologic conditions, such as congestive heart failure, coronary artery disease, or valvular heart disease.
4. The subject has any form of congenital heart disease (repaired or unrepairs; other than a patent foramen ovale).
5. The subject has any ambulatory or orthopedic limitations that would interfere with the ability to perform the activity.
6. The subject has been hospitalized within 30 days of Screening.

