7.1 SCREENING PERIOD (STUDY DAYS -14 TO -1)

A window of up to 14 days is permitted to enroll a subject after Screening. When feasible, Screening assessments should be completed on the same day. Rescreening will be allowed with the Sponsor's Medical Monitor approval. The following assessments for Screening are required prior to initiating the Screening pre-ISWT assessments:

- Informed consent
- Demographics
- Medical history, including PAH history and WHO Functional Class
- AEs (documented from time of informed consent)
- Concomitant medications
- Vital signs (SBP and DBP)
- Assess subject eligibility per inclusion/exclusion criteria

If eligible after the above assessments, the pre-ISWT, ISWT, and ISWT recovery assessments will be conducted. Any significant changes to the subject's medical condition must be documented throughout the course of the study.

7.1.1 *Pre-ISWT*

AEs and concomitant medications will be assessed throughout the study.

The following assessments are required at -15 and 0 minutes prior to activity induction of PAH symptoms:

- PGI-S questions measurements (to be conducted prior to Borg dyspnea score assessment)
- Borg dyspnea score measurement

Pulse oximetry will be started 15 minutes prior to initiating the ISWT and will be performed continuously through the end of recovery during Period 1. The SpO₂ and HR measurements obtained at -15 and 0 minutes (prior to activity) will be recorded in the subject's source documents and eCRF. Subjects receiving supplemental oxygen during the Screening assessment must continue to receive the same flow rate at all subsequent ISWTs. The supplemental oxygen flow rate must be recorded for each activity, as applicable.

Supplemental oxygen therapy must not be introduced for subjects after the Screening assessment, unless there is an urgent medical need in the clinical judgement of the Investigator.

7.1.2 *ISWT*

AEs and concomitant medications will be assessed throughout the study.

The ISWT will be initiated and the following assessments will be performed immediately at the end of the test (within 1 minute of completing):

- PGI-S questions measurements (to be conducted prior to Borg dyspnea score assessment)
- Borg dyspnea score measurement

Pulse oximetry will be performed continuously through the ISWT. The SpO₂ and HR measurements obtained every minute during the ISWT will be recorded in the subject's source documents and eCRF.

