13 ADMINISTRATIVE AND LEGAL OBLIGATIONS

13.1 PROTOCOL AMENDMENTS AND STUDY TERMINATION

Protocol amendments that could potentially affect the safety of participating subjects or that alter the scope of the investigation, the scientific quality of the study, the experimental design, duration of therapy, assessment variables, the number of subjects treated, or subject selection criteria may be made only after consultation between UTC, its designee (Lung Biotechnology PBC), and the Investigator.

All protocol amendments must be submitted to and approved by the appropriate regulatory authorities and IRB/IEC prior to implementation.

A report documenting study termination must also be submitted to and acknowledged by the appropriate IRB/IEC for each study site.

At the end of the study, where applicable, a final report will be provided to the local regulatory agencies.

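### Exclusion criterion 4 bars the repaired-shunt PAH group that inclusion criterion 3 and the SAP admit

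*Protocol*

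**What the plan says.** Inclusion criterion 3, in the protocol synopsis and in 4.1, lists five qualifying etiologies. One of them is "PAH associated with repaired congenital systemic-to-pulmonary shunts", with the repair at least one year old. The lead-in to 4.1 is permissive: "Subjects who meet the following criteria may be included in the study".

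Exclusion criterion 4 in 4.2 reads: "The subject has any form of congenital heart disease (repaired or unrepaired; other than a patent foramen ovale". The synopsis carries the same bar with a typing slip: "any form of congenital heart disease (repaired or unrepairs; other than a patent foramen ovale". The lead-in to 4.2 is mandatory: "The following will exclude subjects from the study".

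The SAP keeps the repaired-shunt group in its population description (3.1) and as an etiology category to be tabulated (6.7.2).

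**The concern.** Two operative eligibility rules give opposite answers for the same patient. Someone who qualifies under inclusion 3 only through a repaired shunt is caught by exclusion 4, because that criterion expressly reaches repaired disease and exempts only a patent foramen ovale.

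The decision is made locally and early. Protocol 3.4 says "Up to 20 US centers that treat PAH subjects will be identified and recruited for this study", and protocol 7.1 places the step "Assess subject eligibility per inclusion/exclusion criteria" ahead of the Screening walk-test assessments. One site could record a screen failure and another could enroll an identical patient, each citing protocol text. The first patient contributes no PGI-S data. The second is a deviation from exclusion 4, which SAP 6.6 requires to be presented and which could cost the subject a place in the Per-Protocol set. SAP 6.1 makes that set depend on the absence of significant deviations and on appropriate inclusion, as judged by the sponsor at database lock. Protocol 10.4 and SAP 7.4 allow results to be looked at during the study, so this judgment could be made with data in view.

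**Working it through.** The plan states no figure on this point, so the check is a comparison of text followed by a count of what depends on it.

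**Step 1: the two rules side by side**

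| Source | Repaired congenital systemic-to-pulmonary shunt |
|---|---|
| Protocol synopsis and 4.1, inclusion 3 | Admitted if repaired at least 1 year ago |
| Protocol synopsis and 4.2, exclusion 4 | Excluded, repaired or not |
| SAP 3.1 | Named as part of the population |
| SAP 6.7.2 | Named as an etiology category |

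The conflict appears in both the synopsis and the body of the protocol, so it is not a slip in one section.

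**Step 2: does anything reconcile them?**

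- Exclusion 2 defers to the etiologies allowed by the inclusion list, but that deference covers exclusion 2 only. Exclusion 4 has no such wording.
- The patent foramen ovale exception does not rescue the group, because inclusion 3 speaks of repaired systemic-to-pulmonary shunts in general.
- No section says that a specific inclusion overrides a general exclusion. The lead-ins point the other way: meeting 4.1 permits entry, and meeting any item in 4.2 prevents it.

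Read literally, the repaired-shunt row of the SAP etiology summary can hold only zeros or protocol deviations among enrolled subjects.

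**Step 3: etiologies affected**

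The five categories in inclusion 3 and SAP 6.7.2 are idiopathic or familial, collagen vascular disease, HIV, anorexigens or toxins, and repaired congenital shunts. One of the five is affected.

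**Step 4: what follows from each site decision**

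- *Screened out at the eligibility check.* No Screening walk test and no PGI-S or Borg data. Under the SAP 6.1 definitions the patient is in none of the Safety, Psychometric Analysis, Full Analysis or Per-Protocol sets, only among all consented subjects.
- *Enrolled.* The subject is in the Full Analysis Set on starting Day 1 procedures, and in the Safety and Psychometric Analysis sets once the Screening walk and ratings are done. Exclusion 4 does not alter those memberships. The Per-Protocol set is the one left open.

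**Step 5: outputs that depend on the Per-Protocol decision**

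Count of outputs in SAP section 11 by population:

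- All 11, Full Analysis 3, Per-Protocol 5, Psychometric 5, Safety 8
- Total: 11 + 3 + 5 + 5 + 8 = 32
- Endpoint outputs (14.2.x): 4 + 3 + 5 + 5 = 17, where 4 is the number of 14.2.x outputs run on all subjects
- Per-Protocol share: 5/32 = 15.6% of all outputs and 5/17 = 29.4% of endpoint outputs

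The five are 14.2.1.2, 14.2.1.4, 14.2.1.6, 14.2.2.2 and 14.2.2.4. Any Per-Protocol count in 14.1.2 would also move. For scale, one subject is 1/40 = 2.5% of the planned enrollment.

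**The case against.** The strongest reply is that this is a drafting overlap with little consequence.

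- **Premise.** The absolute reading needs every repaired congenital shunt to count as congenital heart disease, and the documents define neither term. This stands as a stated assumption. It remains the ordinary reading: exclusion 4 covers any form of the disease, names repaired disease, and was broad enough to need a separate exception for a patent foramen ovale.
- **Intent.** Exclusion 2 defers to the inclusion list, and inclusion 3 specifies a minimum time since repair, so the authors may have meant to admit the group. That bears on intent but does not change what exclusion 4 tells a site to do.
- **SAP text.** SAP 3.1 is a summary that reproduces none of the nine exclusions, and an empty etiology row harms nothing. It is fair that these sections repeat inclusion 3 and are not independent contradictions. They still need to match whatever answer is chosen.
- **Magnitude.** The count of Per-Protocol outputs would be the same for any significant deviation, Per-Protocol analyses are optional under SAP 6.1, and the named known-groups comparisons in SAP 6.13.3 use functional class and cohort, not etiology. All of this is correct. The count limits how far the problem can spread once a subject is enrolled; it does not estimate bias.
- **Existing safeguards.** The sponsor already reviews the Per-Protocol set at lock, and eligibility is confirmed again on Day 1. Neither helps when the criteria being applied disagree.

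These points limit the weight of the finding. None of them removes the conflict.

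**Conclusion.** The concern holds. Inclusion 3 and exclusion 4 contradict each other in both places where the protocol states them, and no text resolves it. The conclusion rests on one assumption, that a congenital systemic-to-pulmonary shunt is a form of congenital heart disease.

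The numerical reach is small. The number of such patients is not given and may be zero, and the sample-size statement and every other stated figure are unaffected. For a subject already enrolled, the main psychometric analyses keep the same membership. It should still be fixed, because it governs who may enter the study at up to 20 centers and leaves the Per-Protocol status of any such subject without a rule.

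**What to change.** The sponsor should reconcile inclusion 3 and exclusion 4, in the synopsis and in 4.1 and 4.2, so that they give one answer for repaired-shunt PAH. SAP 3.1 and 6.7.2 should then be aligned with it. Separately, before database lock, the sponsor should state how any subject enrolled under the conflicting text is classified for the Per-Protocol set. This review takes no position on which criterion is clinically right.

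The wording change is short and needs no new data or analyses. The procedure around it is heavier: protocol 13.1 says changes to "subject selection criteria may be made only after consultation between UTC", its designee and the investigator, and also requires regulatory and ethics approval before implementation. Protocol 12.3 makes each investigator responsible for obtaining the ethics approval. The documents do not show whether enrollment was still open when the SAP was finalized (30 October 2019). If it had closed, amending the criteria would no longer affect who enters, and the useful remaining steps would be the SAP alignment and the classification statement.

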4.3 PRESCRIBED THERAPY

Subjects must not be receiving any prostacyclin analogs/agonists other than inhaled treprostinil for the treatment of PAH. All concomitant medications taken during the conduct of the study, including those taken for AEs, should be recorded in the subject's source documents and transcribed into the eCRF.

5 SUBJECT ENROLLMENT

5.1 TREATMENT ASSIGNMENT

This is an observational study; therefore, no treatment will be provided in the study.

5.2 ENROLLMENT

The same number of subjects will be enrolled into Cohort A (subjects taking inhaled treprostinil therapy) and Cohort B (subjects who are taking other PAH medications [instead of inhaled treprostinil]). Subjects will be assigned to Cohort A or B based on the use of inhaled treprostinil as determined by the Investigator.

Subjects meeting eligibility criteria will be enrolled into the study and assigned a sequential subject number within their cohort.

5.3 SEQUENCE ASSIGNMENT FOR COHORT A

Subjects in Cohort A will be assigned to either Sequence 1 or 2 by the Sponsor.

5.4 BLINDING

Not applicable. This is an observational study without an investigational medicinal product.

6 DRUGS AND DOSING (OR TREATMENT PROCEDURES)

6.1 DRUG DOSAGE, ADMINISTRATION AND SCHEDULE

Not applicable. This is an observational study and no investigational drug will be administered.

